7.9.4 Electrocardiograms and Echocardiograms

Electrocardiogram (ECG) and echocardiogram (ECHO) assessments will be summarized by treatment group using descriptive statistics. For each ECG and ECHO parameter, the baseline and final observations will be presented by treatment group. Additionally, the largest change from baseline QT interval corrected for heart rate, QRS, and PR intervals, the highest value of QT and the largest absolute change for heart rate will be summarized. Descriptive statistics will be calculated for the observed values as well as the change from baseline values.

A table of frequencies of ECG and ECHO abnormalities of interest that occur after baseline as defined in [Appendix Table 5](#) will be generated by treatment. The number and

percentage of patients experiencing the abnormality as well as the total number of abnormalities will be presented. All ECGs and ECHOs with an abnormality will be listed.

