8.2. Exclusion Criteria

A patient who meets any of the following criteria will be excluded from this study.

- 1. Use of any pharmacologic treatment (other than corticosteroids) within 12 weeks of Week 1 that may have an effect on muscle strength or function (e.g., growth hormone, anabolic steroids).
- 2. Previous treatment with ezutromid (BMN 195/SMT C1100) at any time.
- 3. Previous treatment with drisapersen (PRO051) therapy within the last 3 months. To be eligible for the study, patients who were previously treated with drisapersen must be free of any of the following prior to Week 1: a) any active skin lesions related to drisapersen injection; b) renal signs/symptoms (including proteinuria or elevated creatinine/cystatin C); c) the presence of anti-platelet antibodies (to be tested at screening for patients who were previously treated with drisapersen); and d) abnormal platelet count.
- 4. Previous treatment with any other RNA antisense agent or any gene therapy within the last 6 months, or participation in any other DMD interventional clinical study within 12 weeks of Week 1, or use of the shock training system or "STS," or planned use during this study. Concurrent enrollment in any natural history, observational, or biomarker clinical trial is permitted provided the patient's participation in the other trial does not affect any of the assessments performed in the 4658-301 clinical study. For patients in the untreated control group only, continuation in an interventional trial with standard-of-care medication may also be permitted if the patient's participation in the standard-of-care interventional trial does not affect any of the assessments performed in Study 4658-301, and the patient meets all the protocol-required entry criteria.
- 5. Major surgery within 3 months of Week 1, or planned surgery for any time during this study, except for protocol-specified surgeries, as applicable.
- 6. Presence of other clinically significant illness including significant cardiac, pulmonary, hepatic, renal, hematologic, immunologic, behavioral disease, or malignancy.
- 7. Use of any aminoglycoside antibiotic within 12 weeks of Week 1 or need for use of an aminoglycoside antibiotic or statin during the study.
- 8. Have a left ventricular ejection fraction (LVEF) of <50% based on the screening ECHO or QT interval corrected by Fridericia's correction (QTcF) ≥450 msec based on the screening ECG.

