9.7. Prior and Concomitant Medications and Therapeutic Procedures

For both treatment groups, the dosing regimen for oral corticosteroids for treatment of DMD including, but not limited to, prednisolone, prednisone, or deflazacort, should be kept the same throughout the study except for modifications to accommodate changes in weight.

For both treatment groups, the following therapies may be used before enrollment and throughout the study; however, the dosage should be constant throughout the treatment period, unless clinically indicated:

- Oral ACE inhibitors, including but not limited to perindopril and lisinopril
- Oral β-blockers, including but not limited to carvedilol and atenolol
- Angiotensin-receptor blockers, including but not limited to losartan, irbesartan, valsartan, and candesartan
- Oral laxatives, including but not limited to lactulose, Senokot, and Movicol
- Vitamin D and calcium supplements
- Alendronate (Fosamax) or other bisphosphonates used to treat osteoporosis/osteopenia by inhibiting osteoclasts

• Over-the-counter herbal preparations, including herbal supplements, vitamins, minerals, and homeopathic preparations, provided the patient had been on stable doses for 24 weeks before enrollment in this study

Recommendations for selection of medications and interventions during anesthesia include:

- The use of depolarizing muscle relaxants such as succinylcholine are not permitted in any case due to their potential to induce rhabdomyolysis in patients with DMD
- Volatile anesthetics should be avoided if possible, also due to a risk of rhabdomyolysis

Other concomitant medications (e.g., vitamins or other non-RNA antisense medications) may also be taken if, in the opinion of the Investigator, they do not interfere with study assessments and outcomes. Every attempt should be made to keep the dosage constant throughout the study treatment period (i.e., through Week 96).

Introduction of new physiotherapy interventions during the course of the study must be avoided unless the best interests of the patient are at risk. Should a contracture develop during the course of the study, and it is considered in the best interest of the patient to treat the contracture, then any of the following interventions may be used to reduce the contracture, but they must be clearly documented:

- Contracture control devices
- Night splints
- Stretching exercises (passive, active, self)
- Serial casting

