8. CHANGES IN PLANNED ANALYSES

8.1. Changes from Protocol-Planned Analyses

The following changes were made compared to the protocol-planned analyses:

- Comparisons between the eteplirsen-treated group and the untreated control group will not be performed due to the expected very small number of patients in the untreated control group and the differences in the populations between the treated and untreated groups. No hypothesis test, no p-value and no inferential statistics will be made for comparison of eteplirsen treated patients and untreated patients
- CCI [REDACTED]
- The observed values and changes from baseline for clinical laboratory assessments, vital signs and ECG will only be summarized for baseline, the last visit (final observation) and the highest/lowest values. All clinical laboratory assessments, vital signs and ECG results by visit will be in data listing.
- Renamed “predefined change abnormal” to “predefined markedly abnormal” for clinical laboratory tests and other safety endpoints.
- CCI [REDACTED]

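### SAP 7.9.4 summarises the highest uncorrected QT, so the only explicit peak QT level depends on heart rate and no highest post-baseline QTcF is clearly specified (minor)

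*SAP*

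**What the plan says.** SAP 7.9.4 sets out the ECG summaries.

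- For all parameters: "For each ECG and ECHO parameter, the baseline and final observations will be presented by treatment group".
- For extremes, it adds "the largest change from baseline QT interval corrected for heart rate, QRS, and PR intervals, the highest value of QT", together with the largest absolute change in heart rate. The rate-corrected interval is named for the change and plain QT for the peak. The sentence after that provides descriptive statistics for both observed values and changes.
- For outliers: "A table of frequencies of ECG and ECHO abnormalities of interest that occur after baseline as defined in" Appendix Table 5. The QT criteria there are all on QTcF: below 320 ms, above 450, 480 and 500 ms, an increase of more than 60 ms, and age-specific limits of 480 and 500 ms. Abnormal ECGs are listed.

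SAP 8.1 records the departure from the protocol. Observed values and changes for laboratory tests, "vital signs and ECG will only be summarized for baseline, the last visit (final observation) and the highest/lowest values", and results by visit go to listings. Protocol 13.10.2.4 had planned actual values and changes at each visit.

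The entry limit in Protocol 8.2, exclusion criterion 8, is also on QTcF (450 ms or more at screening).

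**The concern.** Uncorrected QT lengthens as heart rate falls, so its maximum over visits tends to come from an ECG with a slow rate, which need not be the ECG with the longest corrected interval. No limit in the readable text applies to uncorrected QT, so the resulting number cannot be compared with any prespecified criterion.

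The peak matters somewhat more here because by-visit ECG summaries were dropped. ECGs are scheduled at Weeks 12, 24, 36, 48, 72 and 96 (Protocol 10.2.7 and 10.2.10), and Protocol Table 4 schedules none in the safety extension. For a patient who completes Week 96, the level at Weeks 12 to 72 reaches a continuous summary only through the highest/lowest statistics. If the peak is on QT, the group distribution of peak QTcF is not explicitly reported. That includes shifts that stay below 450 ms and rise by no more than 60 ms, which Appendix Table 5 does not count.

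**Working it through.** The plan gives no figure to reproduce; this is a descriptive summary.

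**Inputs**
- Correction: Fridericia, the meaning given to QTcF in SAP Appendix Table 5 and the abbreviation list. QTcF = QT / (60/HR)^(1/3), so QT = QTcF × (60/HR)^(1/3).
- Heart-rate range: 60 to 130 bpm, the limits in Appendix Table 5.
- Individual QTcF and heart-rate values: assumptions. The documents report none.

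**Step 1. Dependence on heart rate at fixed QTcF**

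| QTcF (ms) | HR (bpm) | QT (ms) |
|---|---|---|
| 400 | 100 | 400 × (60/100)^(1/3) = 337.4 |
| 400 | 80 | 400 × (60/80)^(1/3) = 363.4 |
| 400 | 60 | 400.0 |
| 450 | 60 | 450.0 |
| 450 | 130 | 347.8 |

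With QTcF unchanged at 400 ms, a fall from 100 to 80 bpm raises QT by 26.0 ms, and a fall from 100 to 60 bpm raises it by 62.6 ms.

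**Step 2. When the highest QT picks the wrong visit**

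Let visit Y have a higher QTcF than visit X in the same patient. The highest QT still selects X when

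HR_Y / HR_X > (QTcF_Y / QTcF_X)^3.

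Take X at QTcF 400 ms and 60 bpm, so QT = 400.0 ms.

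- Y at QTcF 440 ms: (440/400)^3 = 1.331, so X is selected if Y is above 60 × 1.331 = 79.9 bpm. At 90 bpm, QT at Y is 384.4 ms. The highest QT reports 400.0 ms from X; the highest QTcF would report 440 ms from Y.
- Y at QTcF 470 ms: (470/400)^3 = 1.622, so X is selected if Y is above 97.3 bpm. At 110 bpm, QT at Y is 384.0 ms, and X is again selected.

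**Step 3. What the rest of the plan still shows, assuming a baseline QTcF of 400 ms**
- QTcF 470 ms: above 450 ms, and the rise of 70 ms exceeds 60 ms. Appendix Table 5 counts both, and the ECG is listed as abnormal.
- QTcF 440 ms: not above 450 ms, and the rise of 40 ms does not exceed 60 ms, so neither criterion counts it. The 40 ms rise enters the largest-change summary if it is that patient's largest. The level of 440 ms is certain to appear only in the by-visit listing, unless Y is the final observation.

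**Step 4. After the change**

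A highest-QTcF statistic returns 440 ms and 470 ms in these two cases, whatever the heart rate.

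**The case against.** A reader might infer that a real QTcF effect could go unseen, or that the plan ranks a patient with normal QTcF above one whose QTcF is prolonged. The documents support neither. Section 7.9.4 summarises extremes by treatment group and ranks nobody. The same sentence summarises the largest corrected-QT change, Appendix Table 5 grades QTcF at several levels, and every ECG result is listed. This part of the objection stands in full.

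A second argument is that the highest QTcF may already be delivered. A patient's baseline is fixed, so his largest increase in QTcF occurs at the visit with his highest QTcF. The SAP writes largest change for corrected QT but largest absolute change for heart rate, which suggests a signed increase. If the sentence on observed values covers these extremes, the observed QTcF at that visit is the highest one. SAP 8.1 also speaks generally of highest/lowest values. The reading is possible but not explicit, and the one QT level that 7.9.4 names as a highest value is plain QT. A programmer following the text would output uncorrected QT. The word may be loose shorthand for QTcF, which is itself a reason to correct it.

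Third, large heart-rate shifts are not shown to be likely. The plan allows "Oral β-blockers, including but not limited to carvedilol and atenolol", but Protocol 8.1 requires a stable dose for 24 weeks before Week 1, and Protocol 9.7 asks for constant dosage unless a change is clinically indicated. ECGs are taken supine after at least 15 minutes at rest, and heart-rate change is summarised beside QT. This limits how often the wrong visit would be picked, but it does not make uncorrected QT the right peak variable.

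Finally, keeping a QT maximum beside corrected summaries is not an error in itself. That is accepted: the gap is the absence of an explicit QTcF peak.

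**Conclusion.** The point holds as a minor descriptive reporting flaw. As written, the peak statistic in 7.9.4 is on uncorrected QT. It varies with heart rate (26 to 63 ms in the illustration at QTcF 400 ms) and can come from a visit other than the one with the highest QTcF. No highest post-baseline QTcF level is explicitly summarised, although every QT limit in the readable text is on QTcF.

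It is not a hidden safety signal. Patients who cross a QTcF limit remain visible in the counts, the change summary and the listings. Safety analyses are descriptive, and no test or estimate depends on the QT maximum.

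The conclusion rests on reading QT literally and on the readable text alone. The sizes rest on assumed QTcF values and heart rates within the SAP's 60 to 130 bpm limits.

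**What to change.** In SAP 7.9.4, specify *the highest post-baseline QTcF* as the peak statistic; uncorrected QT may be kept as an addition. In the same sentence, name QTcF as the corrected interval and state that the statistic is the largest increase from baseline.

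The cost is one line of SAP text and one parameter in the table program. QTcF is already needed for eligibility and Appendix Table 5, so no new data or derivation is required.

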7.10. Pharmacokinetic Analyses

Individual plasma levels of eteplirsen will be listed with the corresponding time related to eteplirsen administration, and summary statistics will be generated by per-protocol time of collection.

Population PK analysis of plasma concentration-time data of eteplirsen will be performed using nonlinear mixed-effects modeling. PK data from this study may be combined with those from other studies to support a relevant structural model. Available patient characteristics (including demographics, laboratory variables, genotypes, concomitant medications) will be tested as potential covariates affecting PK parameters. The population PK analysis will be presented in a separate technical document.

8. CHANGES IN PLANNED ANALYSES

8.1. Changes from Protocol-Planned Analyses

The following changes were made compared to the protocol-planned analyses:

- Comparisons between the eteplirsen-treated group and the untreated control group will not be performed due to the expected very small number of patients in the untreated control group and the differences in the populations between the treated and untreated groups. No hypothesis test, no p-value and no inferential statistics will be made for comparison of eteplirsen treated patients and untreated patients
- CCI [REDACTED]
- The observed values and changes from baseline for clinical laboratory assessments, vital signs and ECG will only be summarized for baseline, the last visit (final observation) and the highest/lowest values. All clinical laboratory assessments, vital signs and ECG results by visit will be in data listing.
- Renamed “predefined change abnormal” to “predefined markedly abnormal” for clinical laboratory tests and other safety endpoints.
- CCI [REDACTED]

8.2. Changes from Previous Statistical Analysis Plans

The following changes were made compared to the previous SAP (SAP 1.1):

- Updated imputations for Western Blot sensitivity analyses

CCI [REDACTED]

- Added box plot figures for each dystrophin-expression endpoint

10.1. Criteria of Abnormalities

Appendix Table 1 Chemistry Laboratory Abnormalities of Interest

Test	Unit	Predefined Change From Baseline		Markedly Abnormal Criteria
		Decrease	Increase	
Blood urea nitrogen	mmol/L	NA	NA	Value $>1.5 \times$ Baseline and $>$ ULN
Creatinine	μ mol/L	NA	35	Value $>$ ULN
Sodium	mmol/L	8	8	NA
Potassium	mmol/L	1.1	1.0	Value > 5.5 mmol/L or <3 mmol/L
Chloride	mmol/L	9	8	NA
Uric acid	μ mol/L	NA	NA	$>1 \times$ ULN
Calcium ^b	mmol/L	0.30	0.30	NA
AST	U/L	NA	NA	Value $\geq 2 \times$ Baseline Value
ALT	U/L	NA	NA	Value $\geq 2 \times$ Baseline Value
Gamma glutamyl transferase	U/L	NA	NA	Value $> 3X$ Baseline OR $>$ ULN
Alkaline phosphatase	U/L	NA	NA	Value $> 1.5 \times$ ULN
Albumin	g/dL	1	1	$<$ LLN or $>$ ULN
Total bilirubin ^d	μ mol/L	NA	10	Value $> 1.5 \times$ ULN
Lactate dehydrogenase	U/L	NA	NA	Value $\geq 2 \times$ Baseline Value
Creatine kinase	U/L	NA	NA	Value $\geq 2 \times$ Baseline Value
Cystatin C	mg/L	NA	NA	$>$ ULN

^aConvert to SI unit by multiplying mg/dL value by 0.0555

^bmultiply mg/dL value by 0.25;

^cmultiply g/dL value by 10

^dmultiply mg/dL value by 17.1.

ALT = alanine aminotransferase; AST = aspartate aminotransferase; LLN = lower limit of normal; NA = Not Applicable; ULN = upper limit of normal

Appendix Table 2 Hematology Laboratory Abnormalities of Interest

Test	Unit	Markedly Abnormal Criteria
Hematocrit	1	< LLN
Hemoglobin	g/L (or mmol/L)	< LLN
Red blood cell count	trillion/L	< LLN
White blood cell count	10 ³ /L	> 1.5 × ULN or < LLN
Platelet count	10 ⁹ /L	< 150 or < 200 with a decrease from Baseline of at least 100
Basophils (abs)	10 ⁹ /L	> ULN or < LLN
Eosinophils (abs)	10 ⁹ /L	> 1.5 × ULN or < LLN
Lymphocytes (abs)	10 ⁹ /L	< LLN
Monocytes (abs)	10 ⁹ /L	< LLN
Neutrophils (abs)	10 ⁹ /L	> 1.5 × ULN or < 0.000001

abs = absolute; LLN = lower limit of normal; ULN = upper limit of normal

Appendix Table 3 Urinalysis Laboratory Abnormalities of Interest

Test	Markedly Abnormal Criteria
Protein in urine	> 1+
Hemoglobin/blood in urine	Positive (+)
RBC in urine	>0

Appendix Table 4 Vital Sign Abnormalities of Interest

[figure not shown]
Variable	Units	Markedly Abnormal Criteria Lower limit	Markedly Abnormal Criteria Upper limit
Systolic blood pressure	mmHg	< 90	> 140
Diastolic blood pressure	mmHg	< 40	> 90
Pulse rate	beats/minute	< 60	> 130
Respiratory rate	breaths/minute	< 12	> 20
Temperature	°C	< 36.0	> 38.0
Weight	kg	Decrease of 7% or more from Baseline	

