Blood samples for assessing plasma drug concentrations will be obtained at a subset of sites from at least 24 patients in the treated group. On Week 1, a single predose blood sample will be taken within 2 hours prior to the start of administration of the first dose. Both predose and postdose samples will be taken on Weeks 40, 48, 60, 84, and 96 as follows: within 2 hours prior to the start of the infusion, and approximately 5 to 10 minutes, 1 to 2 hours, and 2 to 4 hours after completion of the infusion; at Weeks 48 and 96, samples will also be taken at the end of the infusion prior to flushing the infusion line. Postdose samples alone will be taken on Weeks 8, 16, 24, 32, and 72, approximately 5 to 10 minutes after the completion of the infusion (the approximate time of post-dosing maximum plasma concentration for eteplirsen). Additional post dose samples will be taken on Weeks 8 and 24, approximately 1 to 2 hours after the completion of the infusion and on Week 72 at 2 to 4 hours after the completion of the infusion.

DURATION OF STUDY:

Screening/Baseline Period: up to 10 weeks (not including time needed for genotyping if the patient has not previously been genotyped)

Treatment Period: at least 96 weeks Safety Extension: not to exceed 48 weeks

Safety Follow-up Period: 4 weeks following the last infusion

Total patient participation: approximately 158 weeks

NUMBER OF PATIENTS: Approximately 110 patients will be included in this study, including approximately 90 patients with a Baseline 6MWT distance between 300 and 450 meters (~70 patients in the treated group and ~20 patients in the untreated control group) and approximately 20 patients with a Baseline 6MWT distance >450 meters (~10 patients in the treated group and ~10 patients in the untreated control group).

INCLUSION/EXCLUSION CRITERIA:

Inclusion Criteria:

A patient must meet all of the following criteria to be eligible for this study.

- 1. Be a male with DMD and meet one of the following criteria:
 - Have an out-of-frame deletion that may be treated by exon 51 skipping (e.g., deletions of exons 45-50, 47-50, 48-50, 49-50, 50, 52, 52-63). These patients will be enrolled into the treated group.
 - Have an out-of-frame deletion that is not amenable to treatment by exon 51 skipping but is amenable to treatment by skipping other exons (i.e., whole exon deletions in which the

Sarepta Therapeutics Inc. [name] [contact]

NAME OF FINISHED PRODUCT

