There are currently no disease-modifying treatments for DMD. Existing interventions are largely supportive in nature and include bracing, muscle-stretching exercises to avoid onset of contractures, tendon-release surgery, and eventual wheelchair use and assisted ventilation. Current pharmacologic treatments, such as corticosteroids, focus on alleviation of symptoms, but do not address the underlying cause of the disease. Corticosteroids may prolong ambulation, delay the onset of scoliosis, and improve performance on some measures of clinical function (Beenakker 2005, Biggar 2006, Pradhan 2006). However, their benefits are only temporary, and their use is often limited by numerous side effects, including growth inhibition, effects on pubertal changes, weight gain, behavioral changes, osteoporosis, Cushingoid facies and habitus, and cataracts (Biggar 2006, Manzur 2004).

5.2. Phosphorodiamidate Morpholino Oligomers (PMOs) for the Treatment of Duchenne Muscular Dystrophy

Phosphorodiamidate morpholino oligomers (PMOs) are a class of synthetic molecules based on a redesign of the natural nucleic acid structure. PMOs are distinguished from other antisense oligonucleotide platforms due to the use of a 6-member, synthetic morpholine ring (opposed to the 5-member ribose rings in ribonucleic acid [RNA] and deoxyribonucleic acid [DNA]) to bind the nucleobases, and the morpholine rings are linked through

. These differences impart the stability and safety observed with these compounds in nonclinical and clinical studies.

PMOs are capable of in vivo binding to pre-messenger RNA (pre-mRNA) in a sequence-specific fashion with sufficient avidity to alter the splicing of a pre-mRNA transcript, such as dystrophin. Seventy-five percent (75%) of boys with DMD have out-of-frame deletions that could be amenable to exon skipping therapies (Aartsma-Rus 2009), and modulation of pre-mRNA splicing by exon skipping is currently the most promising molecular intervention in DMD.

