8. PATIENT POPULATION AND SELECTION

8.1. Inclusion Criteria

A patient must meet all of the following criteria to be eligible for this study.

- 1. Be a male with DMD and meet one of the following criteria:
 - Have an out-of-frame deletion that may be treated by exon 51 skipping (e.g., deletions of exons 45-50, 47-50, 48-50, 49-50, 50, 52, 52-63). These patients will be enrolled into the treated group.
 - Have an out-of-frame deletion that is not amenable to treatment by exon 51 skipping but is amenable to treatment by skipping other exons (i.e., whole exon deletions in which the reading frame may be restored by skipping 1 or 2 exons). These patients will be enrolled into the untreated control group.
- 2. Be 7 to 16 years of age, inclusive.
- 3. Have stable pulmonary function (FVC% of predicted ≥50% and not require nocturnal ventilation) that, in the Investigator's opinion, is unlikely to decompensate over the duration of the study.
- 4. Have intact right and left bicep muscles (the preferred biopsy site) or 2 alternative upper arm muscle groups.
- 5. Have been on a stable dose of oral corticosteroids for at least 24 weeks prior to Week 1 and the dose is expected to remain constant (except for modifications to accommodate changes in weight) throughout the study. Note: patients may be allowed to take other (non-RNA antisense or non-gene therapy) medication including angiotensin-converting enzyme (ACE) inhibitors, angiotensin receptor blocking agents (ARBs), β-blockers, potassium, and coenzyme Q, provided they have been on a stable dose for 24 weeks prior to Week 1 and the dose is expected to remain constant throughout the study.
- 6. Achieve a mean distance of 2 separate assessments on 2 consecutive days at the Screening and Baseline visits (prior to Week 1) ≥300 meters on the 6MWT with the 2 consecutive means being within 15% of each other, and with the Screening and Baseline 6MWT conducted 3 to 5 weeks apart. Personal assistance or use of any assistive devices for ambulation is not permitted during the 6MWT.
- 7. Male patients who are in the treated group and are post-pubertal and sexually active must agree to use, for the entire duration of the study and for 90 days post last dose, a male condom and the female sexual partner must also use a medically acceptable form of birth control (e.g., oral contraceptives).
- 8. Have a parent(s) or legal guardian(s) who is able to understand and comply with all the study requirements.

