6.7. Definitions and Terminology

Day 1

Day 1 will be defined as the date of the first eteplirsen dosing for eteplirsen-treated patients, or the Week 1 visit date for untreated control patients.

Study Day

Study day will be defined as Event Date – Day 1 + 1.

Duration on Study

Duration on study will be calculated as the duration in weeks from Day 1 to the date of study completion/discontinuation as recorded on the END OF STUDY eCRF (if completed) or the date of the last study assessment or procedure.

Duration on Eteplirsen

Duration on eteplirsen will be calculated as the duration in weeks from Day 1 to the date of the last eteplirsen administration as recorded on the STUDY DRUG ADMINISTRATION eCRF plus 6 days (ie, [last dose – first dose date + 1 + 6]/7).

Duration in weeks calculated above will be then categorized to 1 of the following intervals: <24, 24 to <48, 48 to <72, 72 to <96, or ≥ 96 .

Planned Dose and Overdose

The body weight-based planned dose was calculated based on most recent weight of previous visits. When calculating the planned dose, the body weight is rounded to a single decimal using conventional rounding rules. While in preparing actual dose, an unconventional rule is applied for calculating the volume of the concentrated drug (50 mg/mL) in milliliter. Any volume of 0.1 or above is rounded up (eg 25.14 mL is rounded up to 26 mL) and any volume below 0.1 is rounded down (eg 25.09 mL is round up to 25 mL). The overdose is defined as any actual dose $>10\%$ above the planned body weight-based dose.

Baseline Visit and Baseline value

Baseline visit will be considered the last visit prior to the initiation of eteplirsen for eteplirsen-treated patients, or the last visit on or before the Week 1 visit for untreated control patients. For any assessment that is taken on 2 consecutive days at baseline visit the base visit (ie, 6MWT, NSAA items and total score, FVC % predicted), the average value will be considered as the baseline value. If the assessment is taken or available only on 1 day at baseline visit, then the value on that day will be used as baseline value.

Change from Baseline

Change from Baseline will be calculated as follows:

$$\text{Change from Baseline} = \text{Post-Baseline Value} - \text{Baseline Value}$$

Percent Change from Baseline

Percent change from Baseline will be calculated as follows:

$$\text{Percent change from Baseline} = (\text{Change from Baseline} / \text{Baseline Value}) * 100$$

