7.9.3 Vital Signs and Other Physical Findings

Vital signs will be summarized by treatment group using descriptive statistics. For each vital sign, the baseline and final observations will be presented by treatment group. Additionally, the largest absolute change from baseline for systolic blood pressure and diastolic blood pressure, the highest value of pulse rate, and the largest absolute change in respiration rate will be summarized. Descriptive statistics will be calculated for the observed values as well as the change from baseline values.

A table of frequencies of vital sign abnormalities of interest that occur after baseline as defined in [Appendix Table 4](#) will be generated by treatment. The number and percentage of patients experiencing the abnormality as well as the total number of abnormalities will be presented. All vital sign values with an abnormality of interest will be listed.

Abnormal physical examination results will be listed.

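### The only weight-loss criterion in SAP Appendix Table 4 is tied to a fixed Baseline, so it becomes less sensitive as growing boys gain weight

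*SAP*

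**What the plan says.** The weight row of SAP Appendix Table 4 reads "Decrease of 7% or more from Baseline". The table has no criterion relative to a previous or highest weight, and none adjusted for age or growth.

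SAP section 7.9.3 puts the row to use. It plans "A table of frequencies of vital sign abnormalities of interest that occur after baseline as defined in" that appendix table, by treatment, and a listing of the values that meet a criterion.

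The reference is fixed by SAP section 6.7: "Baseline visit will be considered the last visit prior to the initiation of eteplirsen for eteplirsen-treated patients". For controls it is the last visit on or before Week 1. Nothing in the SAP updates it later.

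On the population, Protocol section 8.1 requires patients to "Be 7 to 16 years of age, inclusive" and to be on stable oral corticosteroids, with dose changes allowed to follow weight. Protocol section 5.1 lists among the steroid side effects "growth inhibition, effects on pubertal changes, weight gain".

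On duration, the Protocol synopsis gives "Treatment Period: at least 96 weeks Safety Extension: not to exceed 48 weeks", then "Safety Follow-up Period: 4 weeks following the last infusion", and in all "Total patient participation: approximately 158 weeks". Controls are assessed through Week 96 only.

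**The concern.** A percentage drop from a fixed starting weight measures weight loss well when weight is otherwise stable. In a child who is growing, and who takes a drug known to add weight, the starting value soon stops describing where he should be. The flag limit stays at 93% of Baseline while his actual weight moves up and away from it. A boy can then lose a meaningful share of his current weight and still sit above Baseline, so the table records no loss.

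At stake is whether the one stated tabulation aimed at weight loss can detect it in the later part of follow-up. Other summaries may not fill the gap. SAP section 7.9.3 names extreme-value summaries for blood pressure, pulse and respiration but not for weight. SAP section 8.1 moves by-visit vital-sign results into listings.

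**Working it through.** **Follow-up.** Inputs are from the Protocol synopsis: up to 10 weeks of screening, 96 weeks of treatment, up to 48 weeks of extension and 4 weeks of safety follow-up.

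10 + 96 + 48 + 4 = 158 weeks, which reproduces the stated total. Counted from Week 1, the maximum is 158 - 10 = 148 weeks, about 2.8 years (52.18 weeks per year), and only for treated boys who use the whole extension. For controls it is 96 weeks, about 1.8 years.

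**Loss needed for a flag.** Let W be Baseline weight and g the fractional gain since Baseline, so that current weight is W(1+g). The flag limit is 0.93W. The loss from current weight that reaches it is

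L = 1 - 0.93W / [W(1+g)] = 1 - 0.93/(1+g).

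W cancels. For any g above zero, L exceeds 7%, and this needs no growth assumption. The size of the excess does need one, and the documents supply neither Baseline weights nor a growth rate. The gains below are therefore assumed.

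| Assumed gain since Baseline | Loss from current weight needed |
|---|---|
| 0% | 7.0% |
| 5% | 11.4% |
| 10% | 15.5% |
| 15% | 19.1% |
| 20% | 22.5% |
| 25% | 25.6% |
| 30% | 28.5% |

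The same relation by assumed compound annual gain, with g = (1 + annual gain)^(weeks/52.18) - 1:

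| Assumed gain per year | Needed at Week 96 | Needed at Week 144 (treated only) |
|---|---|---|
| 2% | 10.3% | 11.9% |
| 5% | 15.0% | 18.7% |
| 10% | 22.0% | 28.5% |
| 15% | 28.1% | 36.8% |

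**Inverse.** g = 0.93/(1-L) - 1. A needed loss of 15% corresponds to a gain of 9.4%, and a needed loss of 30% to a gain of 32.9%.

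**Illustrations (assumed weights).**
- A boy goes from 30 to 36 kg. His limit is 0.93 × 30 = 27.9 kg, so he must lose 8.1 kg, or 8.1/36 = 22.5%. If he loses 7% of 36 kg he weighs 33.5 kg, which reads as +11.6% from Baseline.
- A boy goes from 50 to 54 kg, a gain of 8%. His limit is 46.5 kg, and the needed loss is 7.5/54 = 13.9%.

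**Weighings available (Protocol Tables 2, 3 and 5).** Treated boys are weighed after Week 1 at Weeks 4 to 48 and 52 to 96, every 4 weeks: 12 + 12 = 24 times. Controls are weighed at Weeks 4, 8, 12, 24, 36, 48, 72 and 96: 8 times.

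**The case against.** The strongest case against the point is that change from Baseline is the SAP's general convention and also appears in other abnormality criteria, so 7% from Baseline may be exactly what was meant. The row feeds a descriptive table and listing and drives no decision. Weight loss has other routes to notice: Protocol section 10.4.2 has clinically significant changes recorded in source documents, adverse events include signs the investigator observes, and by-visit values are listed. Protocol section 13.10.2.2 also planned weight by visit with change from Baseline. SAP section 8.1 restricts by-visit summaries of vital signs, but Protocol section 10.4.2 names weight separately from vital signs, so it is arguable whether the weight summaries were dropped. All of this stands, and it keeps the point small. It does not restore the row's sensitivity.

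A reader might also infer four stronger things that the documents do not support:

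- *Every boy must lose 15-30% by Week 96.* That range holds only for gains of about 9-33%. Entry runs to age 16, and the Protocol lists growth inhibition beside weight gain. A boy who has gained 8% or less needs about 7-14%.
- *The table will show almost no weight loss in later years.* No flag rate can be derived from the documents. Any boy at or below 93% of Baseline is flagged at any visit.
- *The problem runs for three years in everyone.* The 158 weeks include screening, controls stop at Week 96, and the extension can end early.
- *Dosing is affected.* Protocol section 9.3.2 bases the dose on the most recent weight, not on this table.

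A further objection concerns the remedy. A running maximum rises with the number of measurements, so with 24 weighings against 8, noise would produce more flags in the treated group. This stands, and the fix has to deal with it.

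**Conclusion.** The point holds as a minor one. With a fixed Baseline, the loss from current weight needed for a flag is 1 - 0.93/(1+g), which is above 7% for any boy who has gained weight and grows with the gain: 15.5%, 22.5% and 28.5% after gains of 10%, 20% and 30%. The direction follows from the rule alone. The size depends on gains that the documents do not state, and for boys with little gain the effect is slight. The consequence is reduced sensitivity in one row of a descriptive safety table, with no bearing on efficacy or dosing. It merits a change because the change is cheap.

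**What to change.** In SAP Appendix Table 4 and section 7.9.3, keep the existing row and add a second: a decrease of 7% or more from the highest previous on-study weight, Baseline included.

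For the table by treatment group, derive the new row only from visits scheduled in both groups: Baseline/Week 1 and Weeks 4, 8, 12, 24, 36, 48, 72 and 96. In the listing, use all treated-group weights, including those from the extension.

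Common visits equalise the schedule but not attendance. Because the SAP itself reports a large dropout among controls, show the number of boys contributing in each group.

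The cost is one extra derivation and no new data. The downside is some additional flags from measurement noise, since a running maximum tends to pick up high readings. Keeping the from-Baseline row beside the new one lets a reader see the difference.
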